## 4. PROCEDURES AND MEASUREMENTS

### 4.1 Identification and recruitment of participants

We will recruit patients who are referred for clinically indicated cardiac pacemaker procedures. Patients who potentially fulfil the study inclusion criteria and none of the exclusion criteria will be identified and approached by members of their direct healthcare team to discuss study participation. Many patients will be identified by clinical teams during acute admissions to hospital with bradycardia. Clinical teams will alert the study teams within the hospital to facilitate trial enrolment.

### 4.2 Screening and pre-randomisation evaluations

Written informed consent will be obtained before the participant undergoes any screening procedures. If patient is unable to sign the informed consent form themselves due to blindness or other disability which doesn't affect their understanding of the study/capacity, a witness can sign on behalf of the patient. Where verbal consent is used to consent patient to the trial, randomisation cannot occur until the patient physically signs the informed

consent form. All subjects will be assigned a study-specific subject number at the screening visit and the following tests/assessments will be performed:

- Medical History
- Review of clinical echocardiographic data
- Review of clinical ECG and pacing indication
- Concomitant medication
- Pregnancy test (where required) as per standard of care

#### 4.3 Randomisation and Blinding

Randomisation will take place using a fully validated, high quality, real-time electronic data capture system (OpenClinica database). Randomisation will be 1:1 between receiving ventricular myocardial pacing from a lead in the Right Ventricle versus a Physiological Pacing approach. Randomisation will occur once a patient has signed the informed consent form. The randomisation list will be programmed by the statistician using variable block length and stratified by site. Patients will be blinded to treatment allocation in a single blinded fashion. All endpoints will be adjudicated by blinded committee of clinicians with expertise in heart failure.

#### 4.4 Visit Schedule

Visit/Timepoints	Local Sites			Central Trial Hub		
	Screening	Implant	ECHO Sub-study (500 pts)	Follow Up Virtual Visits		
-6 weeks to 0 Day		0	0-6 weeks post implant	24 months (± 1month)	Monthly A (± 7 days)	6 Monthly B (± 7 days)
ENROLMENT:						Final Visit C
Informed Consent	X					
Eligibility Criteria	X					
Demography	X					
Randomisation/Allocation		X				
INTERVENTION:						
Device Implantation		X				
ASSESSMENTS:						
Medical history	X					
Echocardiography	X \$		X	X		
ECG	X E	X *				
Heart rate and cardiac rhythm	X	X				
Concomitant medication	X	X	X	X	X	X
Pregnancy test where required	X					
Post implantation chest radiograph		X				
Pacing check		X			X #	X
Vital Signs		X				
PRIMARY ENDPOINTS:						
Mortality Status					X	X
HF Morbidity					X	X
SECONDARY ENDPOINTS:						
EQ-5D	X				X	X
SF-36	X				X	X
Healthcare Utilisation Assessment					X	X
AF burden					X	X
Percentage Pacing					X	X
Daily Patient Activity					X	X
Patient Reported Symptoms				X	X	X
Device Upgrade					X	X
Adverse Events		X	X	X	X	X
Study End of Visit Form						X

**\$** Taken at screening or within the past 12months

**\*** Pre and Post Implant ECG (1)

**£** Taken at screening or any point prior to implant

**#** Including in-house pacing checks done as per routine SOC, do not have to necessarily coincide with 6 monthly follow-ups, but should be collected and entered onto eCRF when occurring.

(1) for RV pacing implants, post-implant ECG can occur at any time post-implant

**A** The monthly visits are defined as follow-up visits that occur once a month (within  $\pm 7$  days window) from implant

**B** The 6-monthly visits are defined as follow-up visits that occur every 6 months (within  $\pm 7$  days window) from implant

**C** The final follow-up visit ranges from minimum of 3 years (LPLV)

## 4.5 Interventions

Participants will attend the catheter laboratory for their clinically indicated procedure.

**Intervention and comparator:** Physiological pacing will be compared with right ventricular pacing (apical or septal lead locations as per the implanting physicians' normal practice). The approach for physiological pacing will be either His bundle pacing or left bundle pacing at the operator's discretion.

**His bundle pacing:** Conduction system capture will be confirmed using previously defined criteria (see above). If there is evidence of infra-Hisian block during the resting state or whilst pacing at higher heart rates (up to 130 bpm) then either a more distal His pacing position will be attempted or left bundle pacing will be performed.

Left bundle pacing using the technique described by Huang previously defined criteria will be used to confirm left conduction system capture (see above).

An acute pacing threshold of  $>1.5V @1ms$ , or unsatisfactory R wave sensing (less than 1.5 mV) will not be accepted and the lead will be repositioned or an alternative approach for conduction system pacing will be attempted.

In patients in whom conduction system pacing is not possible or pacing parameters are not acceptable a lead should be placed in the coronary sinus to reduce cross-over rates to RV pacing.

Evidence of the achieved physiological pacing response must be submitted for adjudication as to the type of capture achieved. The minimum required data set will include upload of the paced QRS with the pacing output shown, the lead EGM at the final position and evidence of a manoeuvre that demonstrates a transition in capture morphology demonstrating conduction system capture.

All patients will undergo a post-procedure chest radiograph to confirm lead position and rule out a pneumothorax if this is standard of care at the site. An AP image of this will need to be uploaded to the trial hub.

## 4.6 Assessments

### Implant Visit

At the implant visit, after randomisation the following procedures will take place: -

- ECG
- Concomitant medication collection

- Device Implantation
- Post implant chest radiograph (if this is standard of care at the site)
- Pacing Check
- Vital signs

### ECHO Sub study

For patients recruited to the echo sub study echocardiography will be performed at the local site within 6 weeks of the initial implant. Multiple recordings of apical 4 chamber and 2 chamber windows will be obtained for determination of blinded assessment of chamber dimensions, volumes and function. Atrial size and valvular function will be reported too.

ECHOs should be submitted via your site specific OneDrive link. All ECHOs should be identified by patient ID and timepoint.los

### Genetic Sub-study

For patients recruited to the genetics sub-study (optional), a blood sample of 3mls (in a EDTA tube) will be taken for gene sequencing and analysis by a laboratory based at Imperial College London.

The samples will be stored and transported to the central trial hub for analysis. They will be stored in -80 freezers at Imperial College and tracked on the appropriate tracking software (LabVantage or equivalent) according to local governance. Sample tubes will be barcode-labelled with the StudyID and aliquot number. Imperial College Laboratory space is only accessible by security access.

For those participants in the optional genetic sub-study, 3mls of blood will be drawn at either the screening or implant visit. If not taken at this stage, they will be drawn at any other point in the trial.

## **4.7 Follow Up**

Follow up at all UK centres will be conducted by a central trial hub utilising:

1. Online questionnaires and/or telephone contact with the participant or their nominated representative completing questions onto the OpenClinica ePRO database. This will occur every 6 months starting from device implantation.
2. Remote follow-up from a participant's pacemaker where available, downloads will be scheduled every 6 months. Where possible data will be transferred from device companies to the trial team either directly or via the implanting/recruiting centre.
3. For participants residing in England – mortality and hospital statistics will be obtained by data draws every 24 months from nationally held records.

PROTECTHF	Protocol No: 22HH7931	Sponsor: Imperial College London	V9.0 16-Jun- 2025
------------------	--------------------------	-------------------------------------	----------------------

Additionally, the central staff will contact participants if made aware by local study team or by the participant of an adverse events and will follow this up accordingly.

Incidental findings identified as part of the research protocol will be reviewed and reported by the clinical members of the research team. Any incidental findings identified will be communicated to the patient's clinical team as well as their GP as per standard protocol.

In some international centres, patients will be contacted by their local site teams instead of the central trial hub. Some international centres may conduct streamlined follow-up, collecting data on HFH and mortality only. Some international centres may also conduct 1-yearly follow-up instead of 6-monthly follow-up and this may be based on data from a national registry instead of via telephone calls to participants directly.

Participants can withdraw from questionnaire and where this is noted, the applicable participants will be followed up on their medical records only, if participants consents to this. A protocol deviation should be raised where participants want to withdraw from questionnaires.

#### **4.8 Follow Up: In Person Pacing Checks**

While in most centres, virtually all follow-up will be coordinated by the central trial hub, we would like to capture the in-house pacing check data. In-house pacing checks are to be performed as per routine standard of care. Frequency of the pacing checks to be done as per local site standard of care (do not have to coincide with 6 monthly follow-up visits). Information from these pacing checks should be collected and entered onto the OpenClinica database as they occur. If this is not possible, ventricular paced ECG and/ or in-house pacing check report, is to be sent to the central trial hub via NHS email or SharePoint.

#### **4.9 Follow Up Period**

The trial has a planned 3.5 year recruitment window followed by a 3 year follow up period. This means the first recruited participant will have 6.5 years of follow up and the last patient 3 years with estimated median follow up of 4 years for the trial.

For participants residing in England, NHS digital data draws will occur every two years in October. This will continue until the formal end of the trial.

#### **4.10 Endpoints**

##### **Mortality Status and HF morbidity**

This will be determined by direct contact with patient or their nominated representative at 6 monthly intervals. Additional notification may come from reporting of adverse events by the participant or the local study teams. Furthermore, for patients residing in England, mortality and hospital events will also be assessed and confirmed using NHS digital records.

Local study teams may be contacted to request further information from participant medical records, regarding adverse events, reported to the central team.

### Questionnaires

Quality of Life and healthcare utilisation assessments will be performed by telephone/online/post questionnaires. The EQ5D, SF36 and a health resource use questionnaire will be completed at baseline and then every 6 months. The custom health resource utilisation form will enquire about change in employment status due to ill health as well as collate number and type of hospital visits.

### Device Upgrade

Incidence of clinically indicated upgrade to conventional biventricular pacing will be obtained either from direct contact with the participant or their nominated representative at the 6 monthly contact or if reported by local study teams. Clinical adjudication of appropriateness will be considered by a blinded committee, they will meet every 12 months. The committee will review and agree these criteria but will include EF drop to  $\leq 35\%$  or a  $\geq 10\%$  drop from baseline, a raised BNP or a Hospitalisation for Heart Failure.

### Pacemaker Reported Endpoints

Pacemaker parameters, Pacemaker-derived (remotely transmitted) objective metrics including atrial fibrillation (duration  $>6$  minutes) and ventricular arrhythmia incidence and daily patient activity (hours/day stratified by device vendor) will be collected as will percentage pacing. For those participants without remote monitoring a percentage pacing as a minimum will be obtained at least annually from clinical in-office reviews.

For patients with remote monitoring enabled devices we will aim to establish a “trial patient clinic” for read-only access of their data. Alternatively, the device manufacturers including Medtronic, Boston Scientific, Biotronik and Abbott will supply periodic spreadsheets of data for trial patients to the local PIs to be passed to the trial team. A trial patient clinic is a virtual read-only space within each manufacturers’ clinical device platform (CareLink for Medtronic, Merlin for Abbott, Latitude for Boston Scientific and Biotronik Home Monitoring for Biotronik) used as standard of care for remote monitoring of devices. The pacemaker parameters which are transmitted to the device manufacturers’ platforms as part of standard of care will be viewable within a dedicated virtual space on the platform to the research team. Clinical teams will access this information as per routine standard of care and there will be no change to this process. Where this workflow is not enabled, we will rely on the local PIs to pass information on where collected.

### Medication Information

Medication information will also be collected at each contact with study participants so that changes in medication can be tracked.

### Safety Endpoints

Device infections (requiring device extraction), pacing thresholds, need for lead revision or reimplantation, generator change, haematoma and pneumothorax. These events will be regularly reviewed by the trial Data Safety Monitoring Board.

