## 1.2 Need for RCT

Physiological pacing strategies may be associated with slightly longer procedural time, higher thresholds and slightly higher lead related complications than RV pacing which has been the standard of care of >60 years. However, whether these potential issues are offset by the potential benefit of improved cardiac activation and therefore function needs to be determined in an adequately powered RCT. This is what PROTECT-HF aims to do.

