### 2.5 Secondary Endpoints (all adjudicated by blinded endpoint committee)

- Via the pacemaker:
  - a) Atrial fibrillation (duration >6minutes)
  - b) Ventricular arrhythmia incidence
  - c) Daily patient activity (hours stratified by device vendor)

- Incidence of clinically indicated upgrade to conventional biventricular pacing (CRT device)
- Patient quality of life assessed via questionnaires (EQ5D, SF-36 and health resource every 6-months)
- Safety endpoints: Device infections (requiring device extraction), pacing thresholds, need for lead revision or reimplantation, generator change, haematoma and pneumothorax.

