### 6.4 Adverse Event recording

For the purposes of this trial, only adverse events related to the study, defined medically important events and cardiac events and conditions after consent has been obtained will be recorded and reported on the database. Please see the complete list below of adverse events that must be reported. All related and unexpected serious adverse events must be reported as stipulated in the Safety Reporting instructions, regardless of whether they are in the list of defined reportable adverse events. Expected AEs in this population of patients with Heart Failure will include hospitalisations related to arrhythmia, worsening shortness of breath and chest pain. Other expected events include those that are related to known complications of pacemaker insertion. This includes, but is not limited to, lead displacement +/- revision, wound or device infection, pneumothorax, haematoma and deep vein thrombosis. For the purposes of this trial, AEs, both serious and non-serious, as described above, will be followed up according to local practice until the event has stabilised or resolved, or the Follow-up Visit, whichever is the sooner. *This may require the central team to contact local teams, to provide further information from the participant medical records, regarding an adverse event.*

All other adverse events, both serious and non-serious will not be reported and recorded on the study database; however, they must still be documented in the medical notes and followed up as per local practice by clinical teams. They will not be monitored for the purpose of this study.

Adverse Events that must be reported are:

- Heart Failure Hospitalisation (HFH)
- Ambulatory Heart Failure events (e.g., Ambulatory diuretic therapy)
- Suspected Heart Failure Hospitalisation (HFH)
- Device issues:
  - Device infection (requiring device extraction)
  - Device infection (requiring antibiotics, with or without device extraction)
  - Significant rise in pacing thresholds
  - Lead displacement or perforation
  - Lead revision or reimplantation
  - Generator change
  - Haematoma
  - Pneumothorax
  - Inappropriate pacing function
- Device upgrade
- Major bleeding or haemorrhage related to device implant
- Any cardiac related hospital admission
- Any cardiac related events, including but not limited to:
  - Myocardial Infarction
  - Arrhythmia events
    - Atrial Fibrillation
    - Ventricular Arrhythmia
  - EF changes
    - EF drop to  $\leq 35\%$  OR

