    - EF drop to  $\geq 10\%$  drop from baseline
  - Shortness of breath
  - Worsening peripheral oedema
  - Lung atelectasis
  - Pericardial effusion
  - Pleural effusion
  - Chest Pain
  - Changes in cardiac blood markers (BNP, Troponin)
- Any cardiac related Accident & Emergency visit, day-case admission, or unplanned outpatient event or procedure
- Loss of capacity
- Delirium
- Dementia
- Stroke
- Non cardiac death
- Sudden cardiac death (Ventricular Tachycardia / Ventricular Fibrillation arrest)
- Cardiac death

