### 10.4 Data Monitoring Committee

A fully independent Data Monitoring and Ethics Committee (DMEC) will be set up to monitor progress, participant safety, blinding fidelity, operator variability and any ethical issues involved in this trial. They will review trial progress, recruitment rates, safety, and data emerging from other trials and make recommendations to the TSC as to whether there are any reasons why the trial should not continue.

A separate DMEC Charter will be drawn up defining their responsibilities, frequency of meetings and reporting to the TSC.

The DMEC are permitted to have access to the unblinded data for review and any comparisons between groups where appropriate.

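### The safety endpoint list is narrower than the device and procedural complications sites must already report, so the between-arm safety endpoint comparison would undercount procedural harm

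*Protocol*

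**What the plan says.** Section 4.10 (Safety Endpoints) lists "Device infections (requiring device extraction), pacing thresholds, need for lead revision or reimplantation, generator change, haematoma and pneumothorax". Section 2.5 gives the same six items as a secondary endpoint, under a heading that puts all secondary endpoints before a blinded committee. Section 7.3(iii) commits secondary outcomes to model-based analysis.

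Section 6.4 has a longer list of adverse events that sites must report on the trial database. It includes "Lead displacement or perforation", "Pericardial effusion", major bleeding from the implant (as an entry separate from haematoma), and "Device infection (requiring antibiotics, with or without device extraction".

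Section 1.2 accepts that physiological pacing may carry "slightly higher lead related complications than RV pacing" and says the trial has to establish whether benefit outweighs such drawbacks.

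On monitoring, section 4.10 says of the six listed items: "These events will be regularly reviewed by the trial Data Safety Monitoring Board". Section 10.4 says the independent committee "will be set up to monitor progress, participant safety, blinding fidelity, operator variability and any ethical issues involved in this trial" and allows it unblinded data and between-group comparisons.

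**The concern.** The trial has a benefit question and a harm question, and section 1.2 poses both. For harm, the outcome set named in advance is the list in 2.5 and 4.10. That list filters complications by how they were managed: an infection enters if the device came out, and a displaced or perforating lead enters if it was revised or reimplanted, unless the problem shows up as a threshold change. Pericardial effusion has no route in at all.

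This matters in two ways. First, the named safety result would understate how often implantation causes harm, in either arm. Second, section 4.3 blinds patients but not the treating team, and the implanting operator necessarily knows the allocation. Decisions to extract or revise can be influenced by that knowledge. Blinded adjudication afterwards can confirm that a revision took place, but it cannot remove any influence on the decision to revise. Counting the complication itself is less exposed to this.

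**Working it through.** **Step 1: set the two lists side by side.** The protocol gives no rate, power or hypothesis for the safety endpoints, so there is no planned figure to reproduce. The check is a comparison of text.

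| Reportable under 6.4 | Named in 2.5 / 4.10? | What stays uncounted |
|---|---|---|
| Infection treated with antibiotics, extracted or not | Only if extracted | Infection without extraction |
| Lead displacement or perforation | No; enters if the lead is revised or reimplanted | Displacement or perforation without revision |
| Pericardial effusion | No | All, unless another listed item also occurs |
| Major implant bleeding | No; some enters as haematoma | Major bleeding other than haematoma |

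Section 6.4, in its remarks on expected events, itself allows that a lead may displace with or without revision. The uncounted category is therefore one the protocol foresees.

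**Step 2: look for another stated route to a between-arm comparison.**
- Section 7.3(iii) compares implant pacing parameters (thresholds, sensed R wave, impedance) between arms. None of these is a count of the omitted events.
- Section 6.4 classes lead displacement and device infection as expected, so the route in 6.5(v) for related and unexpected serious events would not normally pick them up.
- Section 6.5(vi) has annual reports detail all serious events recorded, without saying by arm.
- Section 10.4 lets the monitoring committee make comparisons, but does not define which.

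**Step 3: scale.** Inputs: 2600 patients (7.2) and 1:1 allocation (section 3), so 2600 / 2 = 1300 per arm. Section 1.1 cites lead complication rates of 2.6% for right ventricular and 2.8% for left bundle pacing.
- 1300 × 0.026 = 33.8 events
- 1300 × 0.028 = 36.4 events

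With counts of this order, a handful of uncounted events in an arm could change the comparison.

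**Step 4: illustration under assumptions.** The protocol gives neither a true excess of complications nor the share of it that would go uncounted. Both are assumed below; the table is not evidence that an excess exists. It takes p1 = 2.6%, fully counted, in the right ventricular arm, and p2 = p1 + excess × (1 − uncounted share), with n = 1300 per arm and two-sided alpha 0.05 (7.3):

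power = Φ{ [ (p2 − p1)√n − 1.96√(2p̄(1 − p̄)) ] / √( p1(1 − p1) + p2(1 − p2) ) }, where p̄ is the mean of p1 and p2.

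Example, 2-point excess, all counted: p2 = 0.046 and p̄ = 0.036, so (0.721 − 0.516) / 0.263 = 0.78 and power is 78%.

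| Assumed true excess | All counted | 25% uncounted | 50% uncounted | 75% uncounted |
|---|---|---|---|---|
| 1 point | 31% | 20% | 12% | 6% |
| 2 points | 78% | 57% | 31% | 12% |
| 3 points | 97% | 86% | 57% | 20% |

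If the uncounted events were equally frequent in both arms, the difference between arms would not move; only the level of harm in each would be understated.

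**The case against.** The strongest reply is that nothing is lost. The omitted events are mandatory reports on the trial database, section 7.3 leaves detailed analyses to the SAP, and tabulating adverse events by arm is ordinary SAP content. That stands as far as it goes: the protocol does not confine safety reporting to the endpoint list, and the events may well be tabulated. But a SAP table would not change the endpoint definition, which 2.5 and 4.10 do state, and adverse event rows do not have the standing of a named, adjudicated endpoint.

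Four stronger readings are tempting, and the documents do not support them.

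- *The monitoring board sees only the six items.* Section 4.10 says these events are reviewed, not that only these are. Section 10.4 gives a general participant-safety remit with unblinded data. (The committee has different names in 4.10, 10.4 and 10.5; that is a naming matter only.)
- *Perforation is a named hazard of the physiological arm.* The left bundle steps in section 3 describe 10-15 rapid turns into the septum and advise caution at low impedance, but never mention perforation. It is named only in 6.4, which covers both arms.
- *The omission favours physiological pacing.* This is plausible for displacement, perforation and effusion, given section 1.2, but it is not shown. The list keeps thresholds and lead revision, where sections 1.1 and 1.2 suggest physiological pacing may do worse (1.1 cites about 7% lead reintervention for His pacing). No reason is given why infection treated without extraction should differ by arm.
- *The bias has a known size.* No rates for the omitted events are given. The 0.2-point gap between the cited 2.8% and 2.6% is background literature, not a difference the trial is designed to judge.

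There is also overlap: displacement or perforation that leads to revision is counted, some implant bleeding is counted as haematoma, and a lead problem that appears as a threshold change is covered by the threshold item.

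**Conclusion.** The point holds as a mismatch between two stated lists. Four kinds of complication that 6.4 requires sites to report are wholly or partly outside the safety endpoints, and two of the six endpoint items use a treatment decision as the threshold for counting. A comparison on the listed endpoints would undercount procedural harm. The direction and size of any between-arm bias cannot be derived from the protocol, and the power figures above hold only under their assumptions. The primary endpoint is unaffected and no data are missing from the design. This is a cheap improvement that makes the safety comparison match the question in section 1.2.

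**What to change.** In 2.5 and 4.10, add these items from 6.4:

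- lead displacement or perforation, whether or not the lead is revised;
- pericardial effusion within a stated period after implant, since 6.4 lists it among general cardiac events;
- major bleeding from the implant procedure;
- device infection needing antibiotics, with or without extraction, reported beside the extraction-only count.

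Compare all of them by arm in the final report and in reports to the monitoring committee. State how one episode is counted when it fits two items (displacement and revision, haematoma and major bleeding, the two infection definitions).

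The cost is protocol wording, a few more table rows and some added event classification. No new data collection is needed, because 6.4 already makes every item mandatory, and no clinical management changes. The streamlined follow-up that 4.7 allows at some international centres may limit completeness for these items, as it may for the existing six.
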